**OBJECTIVES:**

**Purpose**

The primary purpose of the study is to determine the effect of sleep deprivation on neural responses to food odors in the early olfactory and reward-related brain regions, and how these effects are related to appetite-regulating hormones. We will further examine how altered neural responses to food translate to enhanced appetite and food intake, and which brain processes support resilience to sleep-dependent increases in food intake. We will use appetitive food odors in combination with functional magnetic resonance imaging (fMRI) and pattern-based data analysis to test the effects of sleep deprivation on neural responses to food. We will also examine effects of sleep deprivation on appetite levels, odor pleasantness, and *ad-libitum* calorie intake.

**Specific aims and Hypothesis**

**Aim 1. Identify sleep dependent alterations in early olfactory responses to food odors.**

Food odors reliably activate both early olfactory and reward-related brain networks. Orexigenic hormones are enhanced in a sleep-deprived state and have been shown to modulate olfactory sensitivity to food. Here we aim to identify effects of sleep deprivation on early sensory processing of food odors, and how these effects are linked to changes in appetite-regulating hormones. *We hypothesize that fMRI responses to high-caloric food odors will be elevated when subjects are sleep-deprived. Specifically, we predict that sleep-deprivation will alter levels of orexigenic hormones along with early olfactory responses to food odors.* Our setup allows us to deliver appetizing food odors to human subjects undergoing fMRI scanning, and thereby to measure responses to these stimuli in olfactory cortex (i.e., piriform) as well as in reward-related regions (amygdala, orbitofrontal cortex).

**2) Aim 2: Determine the link between sleep-dependent olfactory processing and calorie intake.**

Sleep-restriction has been shown to enhance craving and consumption of high-calorie snacks. Here we aim to determine the relationship between altered hormone levels, neural processing of food odors, and enhanced calorie intake. *We hypothesize that fMRI responses in early olfactory and reward-related brain regions will mediate enhanced food craving and calorie intake. Moreover, we predict that brain processes related to resilience will be represented in the dorsolateral prefrontal cortex, and that these processes are characterized by enhanced connectivity with reward-related brain regions.* After the fMRI scanning session, satiated subjects will be given the opportunity to consume high-calorie snacks *ad libitum* in a controlled environment. In addition, subjects' food intake will be recorded for 24 after the scanning session using dietary diaries. We will compute the total calorie intake and compare it between

sleep-deprived and non-deprived states. Critically, we will use neural mediation analyses to determine how the relationship between sleep-dependent changes in hormone levels and enhanced calorie intake is mediated by neural responses to food odors. This will reveal brain regions in which neural processing of food mediates increased food intake, and thereby identify potential therapeutic targets. We also propose to compare subjects that manage to abstain from excess calorie intake in a sleep-deprived state to those that do not. This will identify brain processes that support resilience to enhanced calorie intake. We predict that such processes will be represented in the dorsolateral prefrontal cortex and will be characterized by enhanced inhibitory connectivity with reward-related regions. Identification of these protective mechanisms may inform future clinical studies in obesity, and may help to establish novel treatment and prevention strategies for weight-gain and obesity, specifically in high-risk populations with disrupted sleep-schedules.

### **BACKGROUND:**

About one-third of adults in the US get insufficient sleep ( $\leq 6$  h per night; 7 h recommended) (1). Habitual sleep deprivation has been associated with adiposity and obesity in both clinical and epidemiological studies (2, 3). A primary reason for weight gain with inadequate sleep is excessive consumption of calories beyond the homeostatic energy requirement (4). Specifically, experimentally induced sleep deprivation increases the desire for foods high in sugar and fat content (5-7), and is related to excessive consumption of calories, especially from energy dense snacks (8, 9). A decline in sleep, paralleled by a steep rise in obesity rates has made it critical to understand the mechanistic link between chronic sleep deprivation and weight gain.

[figure not shown]
Sleep-deprivation has been shown to alter appetite-regulating hormones in humans (10, 11). In particular, sleep deprivation is associated with an increased availability of orexigenic hormones, such as ghrelin (10) and the *endocannabinoids* (2-arachidonoylglycerol (2-AG) and 2-oleoylglycerol (2-OG)) (11). However, how these hormonal alterations affect central processing of food stimuli, and how they result in enhanced food intake with sleep debt is not well understood in humans. Interestingly, studies suggest that orexigenic hormones may regulate appetite and food intake by altering olfactory sensitivity (12-14), hence leading to increased perception and intake of food (15). This would suggest that early olfactory cortices are among the first stages in the neural processing hierarchy at which sleep deprivation alters processing of food-related stimuli.

Food odors are highly potent rewards. In fact, olfactory stimulation is a main component of natural food intake (16, 17) and accounts for most of "flavor" perception (18). Importantly, as discussed above, orexigenic hormones that are influenced by sleep and satiety (11, 15, 19), can modulate olfactory responses (12, 14). Moreover, the primary olfactory (i.e. piriform) cortex has strong, monosynaptic connections with brain areas related to reward, valuation, and decision-making, such as the hypothalamus, amygdala, striatum, and orbitofrontal cortex (OFC) (20). Thus, the early olfactory processes are well positioned to regulate food preference and intake. Indeed, food odors can direct choices toward specific foods, and previous research has reported increased appetite (21, 22), salivation (23), and food preference (21, 22) after exposure to food odors. However, whether sleep-deprivation increases appetite and consumption of high caloric foods by modulating early olfactory processing of food is currently not known. Based on the findings summarized above, *we hypothesize that sleep-deprivation alters neural responses to food stimuli in early olfactory brain regions*, and thereby may elicit a cascade of enhanced processing of food stimuli in reward-related brain regions that ultimately results in excess calorie intake.

Previous human functional magnetic resonance imaging (fMRI) studies have reported changes in reward-related brain regions in response to food-stimuli after sleep deprivation (24-26). However, these studies used pictures of healthy and unhealthy food items, which only capture superficial features of food and, critically, miss an olfactory component. Thus, studies were unable to examine the effects of

sleep-deprivation on early chemosensory processing of food. Moreover, these studies did not examine the effects of sleep-deprivation on appetite-regulating hormones, or how hormonal changes relate to fMRI findings. In the current application, *we propose to study the effects of sleep-deprivation on neural processing of energy-dense food odors in early sensory and reward-related brain regions, as well as on appetite-regulating hormones* (Aim 1). In a subsequent step, we aim to determine how changes neural processing of food odors translate into enhanced food craving and actual calorie intake, and to identify processes supporting resilience to enhanced food intake (Aim 2).

We have the required expertise in neural reward processing (27-29), olfactory psychophysics and neuroimaging (30-36), pattern-based fMRI (3, 37-41), and sleep research (42-44) to successfully conduct all aspects of the proposed experiments. Our preliminary data demonstrate the feasibility of our imaging protocol to measure odor-evoked activity in early olfactory cortices. Specifically, human subjects (N=23) rated the pleasantness of four sweet and savory food odors, and one sweet and one savory odor was selected based on these ratings for each participant (**Fig. 1A**). In the fMRI scanner, a visual cue indicated the type of odor that would be delivered, and subjects were then instructed to sniff the odor (**Fig. 1B**). Every 9-12 trials the association between the visual cue and the delivered odor was reversed. We observed significant food odor-evoked fMRI responses (unpredicted vs. predicted) in piriform cortex, amygdala, and OFC (**Fig. 1C**).

**Figure 1. Food odor-evoked activity in the human brain.** **A.** Two food odors were selected for each subject. **B.** In each trial, the odor type (sweet vs. savory) was predicted by a visual cue. At times, the association reversed and the unpredicted odor was delivered. **C.** Significant fMRI group responses to the delivery of the food odor (unpredicted vs. predicted odor type) in the piriform cortex (PC), amygdala (AMY), and OFC (N=23,  $P < 0.05$ ).

#### **INCLUSION AND EXCLUSION CRITERIA:**

Interested subjects will contact the PI or a research assistant at a phone number or by email indicated on the flyer. During this initial conversation, the PI or research assistant will email an online questionnaire through Google Forms that will be completed by the interested subjects. Responses will be used for screening subjects for inclusion and exclusion criteria. If they meet these initial study criteria, subjects will be invited for an in-person screening process where they will review and sign (either electronically or manually) an Informed Consent form for participation. The participants will fill sleep behavior questionnaires, an MRI-specific safety questionnaire, and undergo an odor-rating task in the lab to determine if they qualify to participate in the study.

**Inclusion criteria:** a) ages 18 – 40; b) right-handed as defined by a modified Edinburgh score  $> 60$  (131); c) Body mass index (BMI) between 18.5 and 24.9; and d) native English speakers.

**Exclusion criteria:** All subjects will be screened for significant neurological or psychiatric disease, chronic medical illness, pulmonary disease, or cerebrovascular risk factors (cardiovascular disease, cerebrovascular disease, hypertension, diabetes, elevated cholesterol, or smoking). Examples in each of these categories would include a history of seizures, multiple sclerosis, meningitis, major affective disorder, obsessive-compulsive disorder, schizophrenia, cancer, chronic obstructive pulmonary disease, severe asthma requiring hospitalization for treatment, renal insufficiency requiring dialysis, etc. Additional exclusion criteria are as follows: a) past or current history of alcoholism or consistent drug use; b) use of medications that affect alertness (e.g., barbiturates, benzodiazepines, chloral hydrate, haloperidol, lithium, carbamazepine, phenytoin, etc.); c) history of major head trauma with sustained

loss of consciousness; d) ongoing or possible pregnancy; e) history of metal working, or injury with shrapnel or metal slivers; f) history of neurosurgery or cardiac surgery; g) history of pacemaker or neurostimulator implantation; i) known smell or taste dysfunction; j) history of significant food or non-food allergy or asthma requiring hospitalization; k) depressed mood (Center for Epidemiologic Studies-Depression Scale score of >15); l) Pittsburgh Sleep Quality Index score >10); m) night work, variable sleep habits, or habitual daytime naps; n) habitual caffeine intake >300 mg/d

Children will not be included in our subject group. Brain organization changes with age. Therefore, to reduce neural variability across the subject group, we plan to limit our studies to adults between the ages of 18 and 40.

**STUDY-WIDE NUMBER OF PARTICIPANTS:**

A total of 40 normal-weight male and female subjects will participate in all aspects of the proposed study.

**STUDY-WIDE RECRUITMENT METHODS:**

Subjects will be recruited from flyers posted around Northwestern, DePaul, and Loyola University, or by email. Interested subjects will contact the PI at a phone number or by email indicated on the flyer. During this initial conversation, the PI or a research assistant will email an online questionnaire through Google Forms that is completed by interested subjects; this is used for screening subjects for inclusion and exclusion criteria. If subjects meet these initial study criteria, they will review and sign an Informed Consent form for participation in the study. Subjects will also review and sign an MRI-specific safety form. A copy of all consent forms will be provided to the subject. Subjects will be paid a total of \$240 for participation in the complete study. If the subject is only able to complete a portion of the study, monetary compensation will be prorated on the basis of procedures completed. The 90-minute fMRI scanning procedure will also be prorated independently in both the sleep deprived and non-sleep deprived stages. Subjects will receive all payment in the form of a check (or in the case of a Northwestern University employee, direct deposit) at the completion of participation in the study, and payment may be subject to tax withholding.

The recruitment process will encourage the participation of women through widespread flyers aimed at the students and staff of Northwestern University. Based on subject recruitment patterns through the Department of Neurology over the last 3 years, we expect equal numbers of men and women to participate in the studies.

[figure not shown]
Similarly, the recruitment process will encourage the participation of minorities through flyers aimed at the students and staff of Northwestern University that have a wide readership. Recent recruitment patterns achieved at the Department of Neurology reflect a diverse ethnic assortment of subjects.

**MULTI-SITE RESEARCH: N/A**

**STUDY TIMELINES:**

Each participant will follow a ~ 6 week within-subject, crossover partial sleep-deprivation protocol to test the effect of sleep deprivation (SD) and non-sleep deprivation (NSD) on neural processing of food odors in sensory and reward related regions (**Fig. 2**). Qualified subjects will be randomly assigned to either participate in the SD or the NSD condition first. Subjects will then undergo a week of sleep stabilization phase to stabilize circadian rhythms for a week. After the sleep stabilization week, the night before the fMRI session, subjects will either sleep normally (NSD, 8 h of sleep between 11 pm and 7 am), or sleep only for 4 h between 1 am and 5 am (SD) at home. All subjects will participate in both sleep conditions (SD and NSD) in randomized order, separated by ~2.5 week washout period. The

evening of the sleep manipulation, subjects will visit the lab to consume dinner and pick up their sleep monitors. We will also provide a take-out breakfast and lunch to be consumed at 8:00 am and 12 noon, respectively. All meals will be provided by the CRU. Subjects will perform an odor-rating task inside the MRI scanner on the same evening. Serial blood samples will be collected for measurement of appetite-regulating hormones. At the completion of the fMRI scan, participants will be provided with snacks in a buffet-style setting where they will have *ad libitum* access to food items corresponding to the odors used during fMRI scanning (sweet and savory high-calorie snacks). They will be instructed to consume as much food as they like. We anticipate to enroll all participants within a 12-month period and plan to complete the study data collection and analyses within a period of 3 years from the date of IRB approval.

**Figure 2. Study design and scanning protocol. A.** Timeline of the sleep-deprivation protocol. All subjects will participate in both sleep conditions (SD and ND), in randomized order. On the scanning day, blood (BD) will be drawn every 30 min. **B.** For each subject, two sweet and two savory high-calorie food odors will be selected and presented during the scanning session, in addition to two non-food odors and trials in which non-odorized air is presented. **C.** Example trial of the fMRI task. After a countdown, an odor is presented, after which subjects have to rate the pleasantness or the intensity of the delivered odor.

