*fMRI scanning protocol.* On the first day of the study, before being assigned to the SD or NSD phase, subjects will rate the pleasantness of six food odors, including three high caloric sweet (caramel, yellow cake, ginger bread) and three high caloric savory odors (potato chips, pot roast, garlic butter). Based on each participant's ratings, we will select two sweet and two savory odors matched in rated pleasantness. We will also include two control non-food odors (fir and celery seed). On the day of fMRI scanning, subjects will arrive at the imaging center at 6 pm and will consume a dinner before entering the scanner. This pre-feeding will satisfy metabolic hunger (i.e., energy requirements), and thus render the fMRI measures more sensitive to sleep-dependent changes in hedonic hunger, i.e., food intake exceeding energy requirements (47). During fMRI data acquisition, odors will be delivered directly to the subject's nose via a MR-compatible olfactometer. Neuroimaging will be performed at the Northwestern University Center for Translational Imaging (CTI) on a state-of-the-art Siemens PRISMA system with a 64 channel head coil, using imaging sequences optimized for signal recovery in olfactory and orbitofrontal cortices (48). Specifically, subjects will perform 4 runs of an odor detection task inside the MRI scanner while blood oxygen-level dependent (BOLD) responses will be acquired with high spatial (2 mm isotropic) and temporal resolution (2000 ms). On each trial, subjects will be cued to sniff, and an odor corresponding to one of the three experimental groups (sweet, savory, non-food) or clean air will be delivered pseudo-randomly. Subsequently, subjects will rate the pleasantness or the intensity (pseudo-randomized) of the delivered odor. Sniffing behavior will be monitored using an MR-compatible breathing belt and a spirometer. A high-resolution anatomical image will be acquired for the purpose of spatial normalization and anatomical localization of the fMRI responses.

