#### **DATA AND SPECIMEN MANAGEMENT:**

Sample size is based upon the requirements for group analysis, particularly when random-effects analyses are performed. Random-effects analyses require a minimum of 14 -18 subjects in each group in order to obtain statistically meaningful fMRI effects. Our target subject number also accounts for attrition in the subject pool due to unanticipated claustrophobia, technical/mechanical issues, or other problems during the fMRI session.

For the statistical analyses, comparisons of subjective appetite ratings and calorie intake between the SD and NSD state will be carried out using paired t-tests. Spearman's correlation analysis will be used to test the relation between appetite ratings, neural responses to food odors, and the total calories consumed. Moreover, we will use whole-brain mediation analysis (51) to identify the brain regions in which neural responses to food odors mediate the link between sleep-dependent changes in hormone levels and enhanced calorie intake. To identify brain mechanisms related to resilience, we will compare fMRI responses to food odors between subjects that manage to abstain from excess calorie intake in a sleep-deprived state to those that do not. We will use fMRI connectivity analyses (psychophysiological interaction, PPI (52)) to test the hypothesis that resilience to enhanced food intake in a SD state is associated with enhanced functional connectivity between the dorsolateral prefrontal cortex and reward-related brain regions (53). We will monitor sniffing using a breathing belt and spirometer, and model trial-by-trial sniff parameters will be included as covariates in all fMRI analyses following established procedures to control for respiration-induced effects.

To preserve subject privacy and confidentiality, all research materials (questionnaires, behavioral testing results, and magnetic resonance imaging data) will be coded by a different study code number unique for each subject, in order to keep the identity and personal information of each subject as confidential as possible. This number will be recorded on all testing sheets instead of the subject's

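### The planned correlation with total calories compares subjects whose buffet menus may differ, without adjusting for menu energy density

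*Protocol*

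**What the plan says.** **Odor selection.** Protocol, Procedures Involved (fMRI scanning protocol): each subject rates "three high caloric sweet (caramel, yellow cake, ginger bread) and three high caloric savory odors (potato chips, pot roast, garlic butter"). From those ratings, "we will select two sweet and two savory odors matched in rated pleasantness". The rating takes place once, "before being assigned to the SD or NSD phase".

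**Buffet.** Protocol, Study Timelines: after the scan, subjects have "access to food items corresponding to the odors used during fMRI scanning (sweet and savory high-calorie snacks"). Procedures Involved repeats this.

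**Between-subject analyses.** Protocol, Data and Specimen Management: Spearman correlation "will be used to test the relation between appetite ratings, neural responses to food odors, and the total calories consumed". The same section plans a mediation analysis for regions where neural responses "mediate the link between sleep-dependent changes in hormone levels and enhanced calorie intake". Aim 2 proposes to "compare subjects that manage to abstain from excess calorie intake in a sleep-deprived state to those that do not". No scale, reference or cut-off is given for enhanced or excess intake.

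**SAP.** Analysis of Food Intake computes total kcal and the energy density of what was eaten. It expresses the change in intake as a percentage of the subject's own non-deprived session and tests that change against zero. The SAP has no section on the correlation, the mediation or the resilience split.

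**The concern.** If menus follow individual odor choices, two subjects who eat the same weight of food can have different calorie totals only because they were served different items. Within a subject this does not matter, because the menu should be common to both sessions. In a correlation across subjects it does.

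There are two possible consequences. The first is noise: variation in menu density dilutes the link between appetite, or brain response, and intake. The sample is small: 40 enrolled with 15% to 25% drop-out leaves 40 x 0.85 = 34 to 40 x 0.75 = 30 subjects. The second is confounding: the odor set determines both the foods served and the odors presented in the scanner. A correlation between neural response and kcal could then partly reflect which set a subject received. The SAP's pattern analysis pools all food odors into one regressor and has no term for the odor set. Pleasantness matching is done within a subject, so it does not equalize menus between subjects.

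**Working it through.** **Number of menus.** C(3,2) x C(3,2) = 3 x 3 = 9.

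**How menu enters each intake measure.** Let g0 and g1 be the grams eaten in the non-deprived and deprived sessions. Let D be the mean energy density of the subject's menu, the same in both sessions and with a similar mix of items eaten.
- Level: kcal = g1 x D. D enters in full.
- Difference: D x (g1 - g0). D rescales the size but never changes the sign.
- Percentage change (SAP): 100 x (g1 D / g0 D - 1) = 100 x (g1/g0 - 1). D cancels.
- Symmetric index (SD - NSD)/(SD + NSD) = (r - 1)/(r + 1), with r = g1/g0. D cancels. For NSD > 0 it ranks subjects exactly as percentage change does.

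**Assumed densities (kcal/g; none are in the documents), in the protocol's odor order.**
- Narrow: sweet 4.0, 3.6, 3.6; savory 5.3, 4.0, 4.5. The lowest menu mean is (3.6 + 4.25)/2 = 3.925 and the highest is (3.8 + 4.9)/2 = 4.35, a ratio of 1.11.
- Wide: the same sweets; savory 5.3, 1.8, 3.5. The lowest is (3.6 + 2.65)/2 = 3.125 and the highest is (3.8 + 4.4)/2 = 4.10, a ratio of 1.31. An extra 40 g then counts as 125 or 164 kcal.

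**Share of variance in log kcal.** Share = var(log D) / [var(log D) + var(log g)]. With all nine menus equally likely, var(log D) is 0.00117 (narrow) or 0.00999 (wide). Grams are taken as log-normal with an assumed CV of 20% or 40%, so var(log g) = ln(1.04) = 0.0392 or ln(1.16) = 0.1484.
- Narrow: 0.00117/0.0404 = 2.9%; 0.00117/0.1496 = 0.8%.
- Wide: 0.00999/0.0492 = 20%; 0.00999/0.1584 = 6.3%.

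These are shares for a non-deprived session. If individual sleep responses add an assumed variance of 0.25² = 0.0625 in the deprived session, the range falls to about 0.5% to 9%.

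**Simulation** (200,000 subjects, same assumptions, log change with mean 0.10 and SD 0.25). The last column is the share of subjects who change side of a median split because of menu.

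| Intake measure | Spearman rho with menu density | Change side |
|---|---|---|
| Deprived-session kcal, narrow | 0.07 to 0.10 | 2.7% to 3.8% |
| Deprived-session kcal, wide | 0.20 to 0.29 | 7.4% to 10.4% |
| Difference in kcal, both sets | 0.01 to 0.03 | 0.5% to 1.3% |
| Percentage change, both sets | about 0 | 0% |

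If excess means eating more than in one's own non-deprived session, menu misclassifies nobody.

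**Possible confounding.** If menu explains a share a of log kcal and a share b of the neural measure, and the two menu effects correlate c, the induced correlation is c x sqrt(a x b). With b assumed at 10% to 30% and c at 0.5 to 1, it runs from 0.5 x sqrt(0.008 x 0.10) = 0.01 to sqrt(0.20 x 0.30) = 0.25. The low end is practically no inflation of the false-positive rate. The high end needs every assumption at its extreme.

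**The case against.** A reader might infer that the correlation, the mediation and the resilience split all compare raw calories. The documents do not support that. Only the Spearman analysis is worded in total calories. The mediation concerns enhanced intake and the split concerns excess intake; both suggest a contrast with the non-deprived state. The SAP's only variable for change in intake is a within-subject percentage, and nothing excludes its use in these analyses. This objection stands, and the point is limited accordingly.

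The size rests on assumptions, which also stands. The wide ratio of 1.31 depends on one item at 1.8 kcal/g. Setting that item to 4.0 gives menu means of 3.675 to 4.225, a ratio of 1.15.

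The confounding path may be weak. The SAP subtracts each subject's decoding maps between sessions, and odors are selected once, so stable odor-set effects should largely cancel if that difference is the neural measure correlated. The protocol does not say that it is.

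The symmetric index adds little to percentage change where both are defined, as the shared ranking shows. Neither is strictly free of menu if sleep loss shifts which items are eaten, and the protocol's Background expects such a shift.

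Finally, the buffet could be read as one common spread covering all study odors. The per-subject selection, and the protocol's Figure 2 legend describing the odors as chosen for each subject, make individual menus the more natural reading, but the text does not settle it.

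**Conclusion.** The point holds for the Spearman correlation: the intake variable is raw, menus probably differ between subjects, and neither document names an adjustment. The expected harm is some dilution, with possible confounding that could be nil. Under the assumed densities the menu-mean ratio is about 1.1 to 1.3 and menu explains roughly 1% to 20% of the variance in log kcal. The sponsor can settle the size from the nutrition labels already in use.

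The mediation and the resilience split are exposed only if their intake terms are taken as a raw deprived-session level or a fixed kcal cut-off. A kcal difference leaves a small scaling effect. The within-subject sleep comparison of calories is not affected, provided the menu was the same in both sessions; the single odor rating before assignment implies this but the plan does not state it. A reader should not infer that the main sleep effect on intake is biased.

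**What to change.** In the protocol's Data and Specimen Management section and in the SAP:

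1. State whether the menu is individual. Keep it the same in both of a subject's sessions or, if sessions have been run, state whether it was.
2. Use a within-subject relative change in buffet kcal in the Spearman, mediation and resilience analyses. This can be the SAP's percentage change or (SD - NSD)/(SD + NSD). The latter stays defined when non-deprived intake is zero and fails only if a subject eats nothing in both sessions.
3. Define enhanced and excess intake on that scale, with the reference and the cut-off.
4. Where an intake level is correlated, use a partial Spearman correlation adjusting for the mean label energy density of the subject's assigned menu. The assigned menu was fixed before assignment; the density of what was actually eaten is itself an outcome.
5. Keep kcal for the within-subject sleep comparison.

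The cost is wording and a reanalysis of data already weighed and labeled. Associations are no longer in kcal, the partial correlation uses one degree of freedom, and density cancels only approximately if the item mix shifts between sessions.
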